9.11 PROs Data Analyses

Patient-reported outcomes will be analyzed using PRO population. Completion rate of each PRO questionnaire (completed questionnaires as a proportion of the expected) will be calculated. Item level missing values will be imputed as per recommendation by the instrument developers.

Changes from baseline (Cycle 1 Day 1) in PRO scores for physical well-being, LymS subscale, FACT-G total, TOI, and FACT-Lym total of FACT-Lym, as well as EQ-5D VAS will be estimated at each cycle for each treatment arm. The changes from baseline in these scores will be compared between the two treatment arms. Patients will be classified as improvement/deterioration based on the established minimally important differences for each measure. Proportion of patients with improvement/deterioration as well as time to improvement/deterioration will be estimated for each treatment arm and compared between the two treatment arms.

The occurrence, severity, and interference (per relevance) of specific symptomatic adverse events selected from PRO-CTCAE, as well as the proportion of patients reporting 'quite a bit' or 'very much' in GP5 item of FACT-Lym will be presented at approximately 3 months and 6 months for each treatment arm, and compared between the two treatment arms.

Full details will be further described in the SAP.

10 Regulatory, Ethical, and Study Oversight/Management Considerations

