I will not disclose information regarding this clinical investigation or publish results of the investigation without authorization from ADC Therapeutics SA.

Signature of Principal Investigator

Date

Printed Name of Principal Investigator

Summary of Changes for Protocol Amendment 3.0

The primary reason for Protocol Amendment 3 is to align the frequency of laboratory evaluations for patients treated with idelalisib with the idelalisib Summary of Product Characteristics (SmPC); to exclude patients with history of hypersensitivity to any of the excipients of study drugs; to align contraception guidance for women of childbearing potential (WOCBP) receiving idelalisib treatment with the idelalisib SmPC; and to extend SAE reporting duration to at least 5 half-lives after the last loncastuximab tesirine dose based on regulatory authority request.

The summary of changes and the rationale in Protocol Amendment 3.0 is as follows:

- Changed treatment cycle length for the idelalisib arm from 3 weeks to 4 weeks and added hematology tests every 2 weeks (Q2W) for the initial 6 months (cycles 1 to 7) and ALT/AST/total bilirubin tests Q2W for the initial 3 months (cycles 1 to 4) of idelalisib treatment.
 - [Section 4.1 Overview & Section 4.2.3 Treatment Period](#): Amended the idelalisib treatment cycle length from 3 weeks to 4 weeks.
 - Schedule of Events: Split Schedule of Events (SoE) table (Table 1) to [Table 1](#) Schedule of Events for Loncastuximab Tesirine Arm and [Table 2](#) Schedule of Events for Idelalisib Arm for a better clarity.
 - Added hematology tests on day 15 for cycles 1 to 7 and AST/ALT /total bilirubin tests on day 15 for cycles 1 to 4 for patients in idelalisib arm in [Table 2](#).
 - PRO-CTCAE questionnaire for patients in the idelalisib arm ends in cycle 7 to correspond to 6-month treatment duration compared to loncastuximab tesirine. Updated the schedule for PRO-CTCAE questionnaire in SoE ([Table 2](#)).
 - [Section 7 Study Assessments and Procedures](#) was revised to reference [Table 1](#) and [Table 2](#) for the study events, where applicable.
- [Section 5.2 Exclusion Criteria](#): Added an exclusion criterion: History of hypersensitivity to any of the excipients of loncastuximab tesirine or idelalisib.

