Coagulation and Urinalysis	7.4.5	X					
HBV, HCV tests	7.4.5	X					
CMV IgG, Antigen or PCR test (all patients) ⁶	7.4.5	X					
HIV tests	7.4.5	X					
Pregnancy test ⁷ , if applicable	7.4.6	X	X	X	X	X	X ⁷ at \geq 9 months post last loncastuximab tesirine dose
12-lead ECG (Triplicate)	7.4.7	X	X (Pre-dose)	X (Pre-dose), EOI- only for loncastuximab tesirine arm		X	
Pre-medication	6.4		D-1 to D2	D-1 to D2	D-1 to D2		

	Protocol Section	Screening	Treatment Period			EOT	Follow-up Period (up to 3 years from EOT) Every 12 weeks
			Cycle 1	Cycle 2	Cycle 3 & Beyond		
(1 Cycle = 3 weeks)							
Day (D)		-28 to -1	1	1	1		
Loncastuximab tesirine Administration (IV infusion)	6.2.2		X	X	X		
PK sample	7.5.1		X (Pre-dose and EOI)	X (Pre-dose and EOI)	X (C3-C6: Pre-dose and EOI; C7, then every other cycle: Pre-dose)	X	
ADA sample	7.5.2		X (Pre-dose)		X (C3, then every other cycle: Pre-dose)	X	X ⁸
Patient Reported Outcomes (EQ-5D-5L)	7.6.1		X	X	X	X	X ¹⁰ Up to 1 year from EOT

	Protocol Section	Screening	Treatment Period			EOT	Follow-up Period (up to 3 years from EOT) Every 12 weeks
			Cycle 1	Cycle 2	Cycle 3 & Beyond		
(1 Cycle = 3 weeks)							
Day (D)		-28 to -1	1	1	1		
Patient Reported Outcomes (FACT-Lym)	7.6.2		X	X	X C3-C18 only	X (only if EOT occurs prior to C19)	
PROs (GP-5 and items selected from PRO-CTCAE) (Complete at home except C1D1)	7.6.3 7.6.4		X⁹ Day 1 & Day 10	X⁹ Day 10	X⁹ C3 – C9 only Day 10		
Concomitant medications	6.9	From ICF signature date or Day -14 whichever is earlier, until at least 30 days after last dose of study treatment					
Adverse events	8	AEs from ICF signature date until at least 30 days after last dose of study treatment; SAEs from ICF signature date until at least 76 days after last dose of study treatment or initiation of new anticancer therapy, whichever is earlier; thereafter only related SAEs					
1 st new anticancer treatment							X
Survival							X

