Abbreviations: ADA: anti-drug antibody; AE: adverse events; BP: blood pressure; β -HCG: β subunit of Human chorionic gonadotropin; C: cycle; C1D1: cycle 1 day 1; [REDACTED] CMV: cytomegalovirus; CT: computerized tomography; ECG: electrocardiogram; ECOG: Eastern Cooperative Oncology Group; EOI: end of infusion; EOT: end of treatment; FACT-Lym: The Functional Assessment of Cancer Treatment-Lymphoma questionnaire; FDG: (18)F-fluorodeoxyglucose; [REDACTED]; HBV: hepatitis B virus; HCV: hepatitis C virus; HIV: human immunodeficiency virus; HR: heart rate; ICF: informed consent form; IV: Intravenous; MRI: Magnetic resonance imaging; PCR: polymerase chain reaction; PK: pharmacokinetics; PRO-CTCAE: Patient-Reported Outcomes Version of the Common Terminology Criteria for Adverse Events; RR: respiratory rate; SAE: serious AEs; Temp: temperature;.

Visit Scheduling Windows:

- Treatment Period: Visit day \pm 3 days (excluding C1D1 which is the reference day).
- EOT: As soon as possible after decision to discontinue the study treatment but preferably at least 30 days after last dose of study treatment unless a new anticancer treatment is planned to be administered before the 30 days, in which case EOT should be conducted before initiation of the new anticancer treatment.
- Follow-up Period: Visit day \pm 14 days.

²Vitals should be taken at pre-dose and EOI for every loncastuximab tesirine dosing visit.

³Positron-emission tomography-computed tomography will be used to perform imaging study. If disease is not FDG-avid at baseline, CT or MRI may be used. Screening imaging must be performed within 4 weeks prior to C1D1 and the same assessment method must be used throughout the study. Week 6 and Week 12 imaging should be performed within \pm 5 days of the scheduled timepoint. All other imaging for disease assessment should be performed within \pm 2 weeks of the

scheduled time point. Imaging for disease assessment should be performed at the scheduled timepoint even if drug dosing is delayed. Additional disease assessments may be obtained, if clinically indicated.

⁴During follow-up period disease assessments to be performed in patients who discontinued study treatment for reasons other than disease progression or initiation of other anti-cancer therapy (except for hematopoietic stem cell transplant).

⁵ \leq 3days prior to administration of study treatment for loncastuximab tesirine arm patients.

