4.2.3 Treatment Period

The treatment period will start on the date when a patient is administered the first dose of study treatment and continues until the end of treatment (EOT) visit (see below).

A treatment cycle is defined as 3 weeks (i.e., 21 days) for patients assigned to loncastuximab tesirine treatment. A treatment cycle is defined as 4 weeks (i.e., 28 days) for patients assigned to idelalisib treatment. Patients will receive either IV loncastuximab tesirine on Day 1 of each cycle, or idelalisib 150 mg BID orally Days 1-28 every cycle. Patients may continue treatment until disease progression, unacceptable toxicity, death, or other discontinuation criteria, whichever occurs first.

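### Section 9.11 indexes FACT-Lym and EQ-5D VAS change only by cycle, but cycles last 21 v 28 days; the between-arm comparison should run on time since C1D1

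*Combined protocol and SAP*

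**What the plan says.** Section 9.11 of the protocol covers three things that matter here.

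- **Change scores.** For physical well-being, LymS, FACT-G total, TOI and FACT-Lym total, and for the EQ-5D VAS: "EQ-5D VAS will be estimated at each cycle for each treatment arm. The changes from baseline in these scores will be compared" between the arms. No week or month is given.
- **PRO-CTCAE and GP5.** These results "will be presented at approximately 3 months and 6 months for each treatment arm" and are then compared, so this part uses calendar time.
- **Detail.** "Full details will be further described in the SAP".

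Section 4.2.3 gives the cycle lengths. For loncastuximab tesirine: "A treatment cycle is defined as 3 weeks (i.e., 21 days". For idelalisib: "A treatment cycle is defined as 4 weeks (i.e., 28 days) for patients assigned to idelalisib treatment".

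In Tables 1 and 2 (Schedule of Events), FACT-Lym is completed on Day 1 of each cycle up to C18 in both arms, and at EOT if that comes before C19. EQ-5D-5L has no cycle cap and continues in follow-up ("Up to 1 year from EOT"). Treatment-period visits have a window of 3 days either side ("excluding C1D1 which is the reference day"). PRO-CTCAE and GP5 end at C9 Day 10 for loncastuximab tesirine and C7 Day 10 for idelalisib. The Summary of Changes explains the second of these: PRO-CTCAE in the idelalisib arm "ends in cycle 7 to correspond to 6-month treatment duration".

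**The concern.** The same cycle number is a different time since baseline in each arm. If the change scores are compared cycle by cycle, any trend over time in these scores, common to both arms, appears as a treatment difference. For FACT-Lym a second effect is added. Cycle visits stop when treatment stops, so the arm observed later at a given cycle number has lost more patients. This second effect is weaker for the EQ-5D VAS, which is also collected after EOT.

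The protocol recognises the issue for its other PRO measures: PRO-CTCAE and GP5 are presented at calendar points, and their last collection day matches across arms. Nothing equivalent is stated for FACT-Lym or EQ-5D VAS change. Comparing PROs between the arms is a stated secondary objective, so the time scale of that comparison should be fixed in advance, the more so in an open-label trial.

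**Working it through.** **Inputs.** Cycle lengths of 21 and 28 days (section 4.2.3); FACT-Lym to C18 and visit windows of ±3 days (Tables 1 and 2); PRO-CTCAE end points (Tables 1 and 2); idelalisib median PFS of 11.0 months, range 8.0 to 14.0 (section 1.2.3).

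**The protocol's own alignment.** With C1D1 as day 1, day d of cycle n falls on study day (n-1) × cycle length + d.
- Loncastuximab tesirine C9 Day 10: 8 × 21 + 10 = 178.
- Idelalisib C7 Day 10: 6 × 28 + 10 = 178.

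The two agree, at a little under 6 months, so the stated alignment reproduces.

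**Same cycle number, Day 1 visits.** Weeks since C1D1 are 3(n-1) v 4(n-1), a gap of n-1 weeks.

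| Cycle | Loncastuximab tesirine | Idelalisib | Gap (weeks) |
|---|---|---|---|
| C2 | week 3 | week 4 | 1 |
| C5 | week 12 | week 16 | 4 |
| C9 | week 24 | week 32 | 8 |
| C13 | week 36 | week 48 | 12 |
| C18 | week 51 | week 68 | 17 |

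**Visit windows.** At C2, day 22 ± 3 gives days 19 to 25, and day 29 ± 3 gives days 26 to 32. They do not overlap. Two windows can close at most 3 + 3 = 6 days, while the gap is 7 days at C2 and grows by 7 days per cycle. On schedule, no cycle after C1 overlaps in time.

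**Visits that do coincide.** Solve 3(n-1) = 4(m-1) with both at most 18:
- week 12: loncastuximab tesirine C5, idelalisib C4;
- week 24: C9, C7;
- week 36: C13, C10;
- week 48: C17, C13.

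**Common FACT-Lym horizon.** The last shared nominal visit is week 48. Loncastuximab tesirine collection ends at C18, week 51. Idelalisib C14 to C18 (weeks 52, 56, 60, 64 and 68), 5 of its 18 cycle visits, lie beyond that.

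**Illustration of who is still observed (FACT-Lym).** Assume identical arms and exponential PFS, and treat progression-free survival as an upper limit on those still attending cycle visits. With 30.4375 days per month, 11.0 months is 47.8 weeks, and the proportion progression-free at week t is 0.5^(t/47.8).
- C9: week 24 gives 0.706 and week 32 gives 0.629, so 71% v 63%.
- C18: week 51 gives 0.478 and week 68 gives 0.373, so 48% v 37%.

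Range at C9 from the other two PFS figures:
- 8.0 months (34.8 weeks): 0.620 v 0.529.
- 14.0 months (60.9 weeks): 0.761 v 0.695.

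Under this assumption the arms are equal at matched weeks by construction. The illustration shows only what a cycle index adds when there is no treatment difference.

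**The case against.** The strongest reply is that the flaw is inferred. One sentence estimates change at each cycle within each arm; the next compares the arms and names no time point, model or summary. A longitudinal model in time would comply with it. A reader might infer that the plan prescribes cycle n against cycle n, and the text does not say so. It defers detail to the SAP, and the text available contains no SAP detail on this analysis, so week-based windows may be set there. This stands, and it limits the strength of the point. It does not remove it, because the only index that is stated does not suit a between-arm comparison.

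Other points that stand:
- **No demonstrated bias.** A reader might infer that the PRO results will be biased by some amount. The documents give no time trend for these scores. The bias in mean change is zero if there is no trend and the patients observed do not change.
- **Gaps are nominal.** Table 4 foresees held loncastuximab tesirine doses, and delays in that arm would narrow the gap. They would also make cycle number a less reliable guide to elapsed time.
- **Selection remains.** The plan assumes CRR of 55% v 15%. If time on treatment also differs, those still observed will differ at matched weeks too.
- **A hard cut at week 48 is not required.** It is one reasonable option. Loncastuximab tesirine C18 (week 51) and idelalisib C14 (week 52) are one week apart, so a windowed analysis can reach about week 51.
- **Some of 9.11 is not cycle-indexed.** Time to improvement or deterioration already runs on a time scale, and the proportions carry no stated cycle. The proportions still need a common horizon if they are cumulative, because one arm has 51 weeks of FACT-Lym collection and the other 68.

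**Conclusion.** The point holds as a specification weakness that should be corrected before analysis. Section 9.11 gives cycle as the only time index for FACT-Lym and EQ-5D VAS change and then compares arms whose cycles differ in length. If the comparison follows cycle number, the arms are nominally n-1 weeks apart: 4 weeks at C5, 8 at C9 and 17 at C18. On-treatment FACT-Lym ends at week 51 in one arm and week 68 in the other.

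This rests on dosing on schedule and on the comparison being made by cycle number, which the text suggests but does not state. The retention figures rest further on identical arms and exponential PFS, and are illustrative.

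The documents do not support a stronger conclusion. They do not show that the PRO comparison will be biased, or by how much. These are other secondary endpoints, outside the sequence that tests CRR and then ORR, so neither of those analyses is affected.

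**What to change.** In section 9.11 or the SAP:

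1. State that between-arm comparisons of FACT-Lym and EQ-5D VAS change use time since C1D1. Use either a longitudinal model in time or windows on actual visit dates, for example around weeks 12, 24, 36 and 48. Keep per-cycle summaries within arm only.
2. Base the FACT-Lym between-arm comparison, including any cumulative proportion improved or deteriorated, on the follow-up common to both arms (about week 48 to 51). Present later idelalisib visits descriptively.
3. Optionally, say whether EOT questionnaires and follow-up EQ-5D-5L assessments enter the comparison. They have no cycle number, but time since C1D1 can place them.
4. Optionally, repeat time to improvement or deterioration on the shared 12-week grid as a sensitivity analysis, since visits are otherwise 3 v 4 weeks apart.

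The cost is wording and slightly more analysis work, with no new data and no schedule change. Idelalisib FACT-Lym visits C14 to C18 drop out of the formal comparison, as does loncastuximab tesirine C18 if the limit is set at week 48. Re-indexing removes the time misalignment. It does not remove selection that arises because the arms differ in time on treatment, and the report should say so.

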⁶CMV tests include CMV IgG and CMV antigen or PCR test at screening visit for all patients.

⁷Serum or urine β -HCG test to be done on every visit at local lab if applicable. If the urine pregnancy test is positive, a serum β -HCG test is required for confirmation. Remote pregnancy test is acceptable when patient has no required site visit planned during follow-up period. Additional tests may be obtained, if needed.

⁸Only patients who test positive for ADAs may be asked to provide additional ADA samples every 12 weeks until the ADA titer falls to the baseline level.

⁹Patients will complete PRO-CTCAE items and GP-5 at study site on C1D1; at home on Day 10 (\pm 2 day) of each cycle for up to Cycle 9.

¹⁰In the event that patients complete follow up visit at home instead of being on site, EQ-5D-5L will be completed on Visit day (+2 days).

Table 2. Schedule of Events for Idelalisib Arm

(1 Cycle = 4 weeks)	Protocol Section	Screening	Treatment Period		EOT	Follow-up Period (up to 3 years from EOT) Every 12 weeks
			Cycle 1 to Cycle 7	Cycle 8 & Beyond		
Day (D)		-28 to -1	1	15	1	
Informed consent	7.1	X				
Randomization	4.2.2		X C1 only (D-1)			
Eligibility criteria	5	X				
Demography	7.2	X				
Medical/Cancer history	7.2	X				
Physical examination	7.4.1	X	X		X	X
ECOG performance status	7.4.2	X	X		X	X
Height	7.4.3	X				
Weight	7.4.3	X	X		X	X
Vital signs ² (BP, HR, RR, Temp)	7.4.4	X	X		X	X
Disease assessment ^{3,4}	7.3	Screening, 6 weeks and 12 weeks after C1D1, then every 12 weeks until 2 years from C1D1, then every 6 months.				
Hematology ⁵	7.4.5	X	X	X	X	X
Chemistry ⁵	7.4.5	X	X	AST/ALT/total bilirubin - C1 to C4 only	X	X
Coagulation and Urinalysis	7.4.5	X				
HBV, HCV tests	7.4.5	X				
CMV IgG, Antigen or PCR test (all patients) ⁶	7.4.5	X				
CMV Antigen or PCR test (for patients with positive CMV tests or history of CMV infection) ⁷	7.4.5		X		X	X
HIV tests	7.4.5	X				
Pregnancy test ⁸ , if applicable	7.4.6	X	X		X	X

	Protocol Section	Screening	Treatment Period		EOT	Follow-up Period (up to 3 years from EOT) Every 12 weeks
			Cycle 1 to Cycle 7	Cycle 8 & Beyond		
(1 Cycle = 4 weeks)						
Day (D)		-28 to -1	1	15	1	
12-lead ECG (Triplicate)	7.4.7	X	X C1-C2 only (Pre-dose)			X
Idelalisib Administration	6.2.2		Twice daily orally			
Patient Reported Outcomes (EQ-5D-5L)	7.6.1		X		X	X ¹⁰ Up to 1 year from EOT
Patient Reported Outcomes (FACT-Lym)	7.6.2		X		X C8-C18 only	X (only if EOT occurs prior to C19)

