³Positron-emission tomography-computed tomography will be used to perform imaging study. If disease is not FDG-avid at baseline, CT or MRI may be used. Screening imaging must be performed within 4 weeks prior to C1D1 and the same assessment method must be used throughout the study. Week 6 and Week 12 imaging should be performed within \pm 5 days of the scheduled timepoint. All other imaging for disease assessment should be performed within \pm 2 weeks of the scheduled time point. Imaging for disease assessment should be performed at the scheduled timepoint even if drug dosing is delayed. Additional disease assessments may be obtained, if clinically indicated.

⁴During follow-up period disease assessments to be performed in patients who discontinued study treatment for reasons other than disease progression or initiation of other anti-cancer therapy (except for hematopoietic stem cell transplant).

⁵Safety lab sample collection on visit days may occur at any time during the visit.

⁶CMV tests include CMV IgG and CMV antigen or PCR test at screening visit for all patients.

⁷CMV antigen or PCR test for patients with positive CMV serology or history of CMV infection who are receiving treatment with idelalisib.

⁸Serum or urine β -HCG test to be done on every visit at local lab if applicable. If the urine pregnancy test is positive, a serum β -HCG test is required for confirmation. Additional tests may be obtained, if needed.

⁹Patients will complete PRO-CTCAE items and GP-5 at study site on C1D1; at home on Day 10 (\pm 2 day) of each cycle for up to Cycle 7.

¹⁰In the event that patients complete follow up visit at home instead of being on site, EQ-5D-5 will be completed on Visit day (+2 days).

1 Introduction and Background

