2.2 Rationale for Dose Selection

Loncastuximab tesirine will be administered intravenously (IV) at a dose of 150 $\mu\text{g}/\text{kg}$ every 3 weeks for 2 doses, then at a dose of 75 $\mu\text{g}/\text{kg}$ every 3 weeks at the subsequent doses.

The initial dose of 150 $\mu\text{g}/\text{kg}$ every 3 weeks (Q3W) was based on the observation that response rate in patients treated in the Phase 1 trial appeared to increase with increasing exposure, but toxicity was substantially increased at 200 $\mu\text{g}/\text{kg}$ compared to lower dose levels. Thus, 150 $\mu\text{g}/\text{kg}$ was chosen as the highest initial dose with acceptable toxicity. The dose reduction after 2 cycles was based on the fact that a substantial portion of patients treated on the Phase 1 trial required dose reduction after 2 or more cycles, usually as a result of prolonged dose delays

because of adverse events (AEs). Decreasing the dose after 2 cycles was intended to reduce the incidence of dose delay and reduce the need for further dose reduction. This dosing regimen has been used in 145 patients in a Phase 2 study of loncastuximab tesirine in patients with R/R diffuse large B-cell lymphoma (R/R DLBCL) and appears to be well-tolerated with a manageable toxicity profile and comparable efficacy to that achieved in a similar patient population in Phase 1.

3 Study Objectives and Endpoints

Table 3. Study Objectives and Endpoints

Objectives	Endpoints
Primary	
To evaluate the efficacy of single agent loncastuximab tesirine compared to idelalisib in patients with relapsed or refractory follicular lymphoma.	Complete response rate (CRR) according to the 2014 Lugano classification as determined by central review in patients with FL. Complete response rate is the proportion of patients with a best overall response (BOR) of complete response (CR) assessed prior to any subsequent anticancer treatment.
Secondary	

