6.3 Study Treatment Assignment and Dosing

- Patients who are eligible will be randomized via Interactive Response Technology to either of the study treatment arms, loncastuximab tesirine or idelalisib in a 2:1 ratio. Loncastuximab Tesirine Arm: Administration of loncastuximab tesirine will be performed by the Investigator or a qualified designee. Patients will receive a 30 minutes IV infusion of loncastuximab tesirine on Day 1 of each cycle (150 µg/kg Q3W for 2 cycles, then 75 µg/kg Q3W for subsequent cycles).
Refer to [Section 6.4](#) for premedication and [Section 6.8](#) for supportive care.
- Idelalisib Arm: Patients will receive 150 mg idelalisib tablet orally BID. Please refer to [idelalisib prescribing information](#) or [idelalisib SmPC](#) for detailed instructions.

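### Section 9.11 names only about 3 and 6 months for comparing PRO-CTCAE and GP5, so the forms from the two 150 µg/kg cycles, and all forms from patients who stop early, enter neither named comparison

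*Combined protocol and SAP*

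**What the plan says.** Comparing the arms on patient-reported outcomes is a secondary objective, and the occurrence, severity and interference of selected PRO-CTCAE symptoms is one of its endpoints (Section 3, Table 3).

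- **Collection.** Both instruments are completed at Cycle 1 Day 1 and then on Day 10 "of each cycle for up to Cycle 9" in the loncastuximab arm (Table 1, footnote 9) and "of each cycle for up to Cycle 7" in the idelalisib arm (Table 2, footnote 9). The PRO-CTCAE/GP5 row has no entry at end of treatment or in follow-up in either table.
- **Analysis.** Section 9.11 says the PRO-CTCAE results, and the proportion in the two highest GP5 response categories, "will be presented at approximately 3 months and 6 months for each treatment arm, and compared between the two treatment arms". In the same section, the FACT-Lym scores and EQ-5D VAS are to be estimated at each cycle. Section 9.11 leaves further detail to the SAP.
- **Dose.** Loncastuximab is given at "150 µg/kg Q3W for 2 cycles, then 75 µg/kg Q3W for subsequent cycles" (Section 6.3). Idelalisib has one scheduled dose throughout.
- **Reason for the step.** Section 2.2 explains that "a substantial portion of patients treated on the Phase 1 trial required dose reduction after 2 or more cycles", usually after prolonged delays for adverse events.

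**The concern.** The loncastuximab regimen has two phases, and the protocol collects patient-reported symptoms in both. The two time points named for analysis lie in the second phase only. A reader of the planned tables would learn how patients still on treatment felt at the lower scheduled dose. They would not learn how patients felt in the first two cycles, or what those who stopped early had reported before stopping.

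Such patients can still belong to the Patient-reported Outcomes Population, which needs only a baseline and one post-baseline questionnaire (Section 9.2). Section 9.11 provides for missing items but not for absent forms. At stake is whether this secondary endpoint describes the regimen as scheduled or only its later part among those who remain.

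**Working it through.** **Inputs.** Cycles last 21 days in the loncastuximab arm and 28 days in the idelalisib arm (Section 4.2.3). The dose changes at Cycle 3 (Section 6.3). Forms are due on Day 10 of each cycle (Tables 1 and 2). One month is taken as 30.44 days, so 3 months is day 91 and 6 months is day 183.

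**The plan's own figure.** The Amendment 3.0 summary of changes says that ending the idelalisib forms at Cycle 7 corresponds to 6 months of treatment. Day of form = (cycle − 1) × cycle length + 10.

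- Idelalisib Cycle 7: 6 × 28 + 10 = day 178.
- Loncastuximab Cycle 9: 8 × 21 + 10 = day 178.

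178 / 30.44 = 5.85 months, so the statement is reproduced and the last forms align.

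**All Day-10 forms on schedule**

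| Cycle | Loncastuximab day (µg/kg) | Idelalisib day |
|---|---|---|
| 1 | 10 (150) | 10 |
| 2 | 31 (150) | 38 |
| 3 | 52 (75) | 66 |
| 4 | 73 (75) | 94 |
| 5 | 94 (75) | 122 |
| 6 | 115 (75) | 150 |
| 7 | 136 (75) | 178 |
| 8 | 157 (75) | – |
| 9 | 178 (75) | – |

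**Which forms are used.** Cycle 3 starts on day 2 × 21 + 1 = 43. The forms nearest 3 months are loncastuximab Cycle 5 and idelalisib Cycle 4, both on day 94. Those nearest 6 months are Cycle 9 and Cycle 7, both on day 178. Both loncastuximab forms are in the 75 µg/kg phase, and the two forms under 150 µg/kg (days 10 and 31) are not used.

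**Does the reading of 'approximately' matter?** No. Every loncastuximab form from day 52 onward is at 75 µg/kg by schedule. To be still on 150 µg/kg at day 91, a patient would need about 91 − 43 = 48 days of accumulated delay before Cycle 3.

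**Early stopping.** With no form at end of treatment or later, a patient who stops before about 3 months has no form at either named time point. The documents give no discontinuation rate for either arm. As an illustration only, assume exponential progression-free survival in the idelalisib arm, with treatment stopping at progression. The proportion progressed or dead by month t is 1 − exp(−ln 2 × t / median). Section 1.2.3 gives a median of 11.0 months, with 8.0–14.0 beside it:

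| Median (months) | By 3 months | By 6 months |
|---|---|---|
| 8 | 23% | 41% |
| 11 | 17% | 31% |
| 14 | 14% | 26% |

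Stops for toxicity would come on top. No such figure can be formed for loncastuximab, whose median was not reached in Phase 1.

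**The case against.** **The SAP may fill the gap.** Section 9.11 does not forbid other summaries, and no SAP text was available to check. This stands as a limit: the documents show that the protocol does not commit to using the early forms, not that they will go unused. But the same section specifies per-cycle estimates for FACT-Lym and EQ-5D VAS and two time points for PRO-CTCAE and GP5, so the protocol states a narrower rule here.

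**Other measures cover the early cycles.** This also stands. FACT-Lym physical well-being and the other scores are compared by cycle, with visits directly after each of the first two loncastuximab cycles. FACT-Lym, which contains GP5, is also collected at end of treatment if that comes before Cycle 19. Treatment-emergent adverse events are summarised from first dose (Section 9.8.1). A reader might therefore go too far in inferring that the early cycles are lost to the tolerability assessment as a whole. What is missing is the PRO-CTCAE symptom detail, and GP5, for which Section 9.11 names no summary from the FACT-Lym visits.

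**The direction of bias is unknown.** A reader might infer that the two time points favour loncastuximab because its dose is front-loaded. The documents do not support that. They contain no symptom data by cycle, and reductions needed after two or more cycles fit toxicity that emerges or accumulates later just as well. Selection by early stopping acts in both arms, and loss of early idelalisib leavers could flatter idelalisib.

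**Conclusion.** The point holds for PRO-CTCAE and GP5 only. Section 9.11 commits to 2 of 9 loncastuximab and 2 of 7 idelalisib Day-10 forms. Both forms completed under 150 µg/kg, and all forms from patients who stop before about 3 months, fall outside the named comparisons. This rests on the scheduled cycle lengths and on the protocol text alone.

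The size of any resulting bias cannot be given. A reader might take the first two cycles' share of the scheduled dose to Cycle 9, 300 of 825 µg/kg (36%), as its measure, but a share of dose is not a share of symptom burden. The attrition range above is likewise an assumption about progression or death, not an estimate of toxicity stops.

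The endpoint lies outside the sequence that tests complete response rate and then overall response rate, so no primary or key secondary conclusion depends on it. The change is still worth making before analysis, because it replaces a stated rule with a fuller one at little cost.

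**What to change.** In Section 9.11 and the SAP:

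1. Present PRO-CTCAE items and GP5 by arm at every collected Day-10 form, placed on calendar time and including Cycles 1 and 2, with the number of forms expected and completed at each.
2. Add, for all patients in the Patient-reported Outcomes Population over a common window to day 178, the worst post-baseline PRO-CTCAE score adjusted for baseline, and the proportion ever in the two highest GP5 categories. Forms completed before early discontinuation then count.
3. Because the arms have 9 and 7 forms, add a sensitivity version restricted to calendar-matched forms: day 10; day 31 (loncastuximab) against day 38 (idelalisib); day 94; day 178.
4. State that patients who stop early have fewer forms, so that neither version gives them equal opportunity to report a symptom.

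The cost is protocol and SAP wording and a few extra tables, with no new visits, data or patients. The drawback is that the worst-score summary depends on how many forms a patient completed, so it should be read as descriptive.
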